**Safety and Feasibility of Transcranial Direct Current Stimulation to Enhance Auditory
Rehabilitation in Cochlear Implant Recipients**

Document Date: 11/09/2022

NCT04908631

**Safety and Feasibility of Transcranial Direct Current Stimulation to Enhance
Auditory Rehabilitation in Cochlear Implant Recipients**

Sponsor:	PI – Department of Head and Neck Surgery & Communication Sciences
Funding Source:	MEDx
Protocol Source:	PI – Department of Head and Neck Surgery & Communication Sciences
Duke IRB#:	Pro00107525
IND#:	N/A
Principal Investigator [name], MBA, FACS Department of Head and Neck Surgery & Communication Sciences [REDACTED]	Study Coordinator [name] HNSCS [REDACTED]
Sub Investigator(s) [name] [REDACTED]	[name] HNSCS [REDACTED]
[name], AuD, PhD [REDACTED]	[name] Brain Stimulation and Neurophysiology [REDACTED]
[name], AuD, CCC-A [REDACTED]	Regulatory Coordinator [name] [REDACTED]
[name] [REDACTED]	Data Manager [name] [REDACTED]
See IRB submission for a detailed list of study personnel.	
Version date:	11/9/2022

1) **Protocol Title:** Safety and Feasibility of Transcranial Direct Current Stimulation to Enhance Auditory Rehabilitation in Cochlear Implant Recipients

2) **Purpose of the Study:**

- a) To evaluate the safety and feasibility of reliable Transcranial Direct Current Stimulation (tDCS) administration at home in combination with home-based auditory training therapy and practice in Cochlear Implant (CI) patients
- b) To evaluate changes in speech perception performance after a 4-week intervention consisting of tDCS combined with auditory rehabilitation and training.

3) **Background & Significance:**

[figure not shown]

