Auditory training methods: Subjects will be provided customized auditory training program using materials from two existing computer-based auditory training programs that can be completed in the home. Specifically, we will use consonant and vowel discrimination and recognition modules from Speech Banana to focus on bottom-up processing tasks. This will allow for practice in discriminating between letters/words (e.g., bat/pat/mat or hid/hood/had). Additionally, modules from the Sound Success program

will be used, which focuses on understanding sentences/conversations in quiet and in noise using different talkers. The latter program also allows the patient to practice listening in familiar contexts (e.g., topics on weather, shopping, and family life). Both programs use an adaptive approach such that the difficulty of training stimuli is adjusted based on performance. Participants will be asked to bring their personal laptop or tablet to the baseline visit (if applicable) so they can download the auditory training software and conduct a practice session before leaving the clinic.

Transcranial Direct Current Stimulation (tDCS): We will use a device that was designed and validated to allow safe and reliable tDCS delivery at home (1x1 tES mini-CT, Soterix Medical, USA). This tDCS system incorporates a customizable headgear for individualized electrode placement and disposable, snap-in electrodes that are easy for the patient to apply at home without assistance. The device also allows the clinical team to control and monitor the home use by the patient. Based on the reports of listening related functional brain imaging (Price 2012), and transcranial stimulation studies (Heimrath et al. 2016), we will deliver anodal stimulation (positive electrode over target) of the primary auditory cortex contralateral to the CI implant.

Patient Reported Outcome Measures will be collected: Speech, Spatial, Qualities of Hearing (SSQ-12), and Cochlear Implant Quality of Life Questionnaire (CIQOL) will be collected at baseline, and the 1 month and 6 month follow-up visits.

An adverse event questionnaire will be collected continuously during the 4 week auditory training sessions and reviewed during each of the weekly tele-visits with a member of the study team.

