Hearing and Speech Evaluation: Hearing thresholds and speech perception performance will be measured during the baseline visit, and 1 month and 6 month follow up visits using standard, validated and standard word and sentence lists presented in quiet and in noise (AzBio Quiet, AzBio +5/+10dB; CNC 50-item list) while the patient is wearing an appropriately programmed CI alone and/or with appropriately fitted contralateral hearing aid (if this is typically worn by the patient).

5) Study Schedule:

Visit 1/Baseline:

Subjects will undergo a screening visit to determine eligibility. The screening visit may be combined with a standard of care visit for patients already being seen for cochlear implant evaluation. Each participant will sign an informed consent before committing to any study-related tests or procedures and will include the following assessments:

- Obtain and document consent from potential participant on informed consent form (ICF).
- Conduct baseline hearing threshold and speech perception testing using standard audiological procedures (e.g., AzBio Quiet, AzBio +5/+10dB; CNC 50-item list) for screening for eligibility and baseline assessment
- Obtain patient reported outcome questionnaires (SSQ-12 and CIQOL)
- Auditory training and assignment of home-based personalized, computer-based rehabilitation/practice plan
- Orientation to tDCS equipment, determination of appropriate stimulation levels and electrode placement

- Conduct integrity evaluation of device using telemetry during initial tDCS trial.
- Repeat subset of speech perception assessment before, during and after the initial tDCS application.
- Instructions for completion of electronic daily diary to record adverse events and compliance of auditory training

The tDCS current will be programmed to 2.5mA prior to the start of integrity testing. If 2.5mA is intolerable, then the current will be reduced to 2.0mA. If a participant is still not able to tolerate 2.0mA, then this will be considered a screen fail and the subject will be removed from study.

Study participants meeting the screening criteria upon completion of the baseline visit will continue on study. Enrolled participants will be given a tDCS device to take home to complete study procedures with instructions to return it at the 1 month post-treatment visit to be completed in person.

Weeks 2-5 (Visits 2 – 5)

During the 30-day treatment period, subjects will be expected to complete the following:

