- Complete daily web-based auditory training with tDCS stimulation for 30-minute sessions, at least five times per week for 4 weeks.
- Completion of a daily diary to record compliance of auditory training with tDCS, as well as to document adverse events that may occur during or after the sessions.
- Video visits will be conducted at least weekly by a member of the research team, starting more frequently in the first week, to provide technical assistance as needed, review reported adverse events, and give reminders regarding completion of the daily diary.

One-Month post-treatment (Visit 6)

Participants will be asked to return at the end of the 30-day treatment period for an in-person visit and undergo the following assessments:

- Hearing threshold and speech perception testing using standard audiological procedures (AzBio Quiet, AzBio +5/+10dB; CNC 50-item list)
- Obtain patient reported outcome questionnaires (SSQ-12 and CIQOL)
- Conduct integrity evaluation of device using telemetry
- Review of adverse events
- Return tDCS device

Six-Month post-treatment (Visit 7)

Participants will be asked to return for an in-person visit and undergo the following assessments:

- Hearing threshold and speech perception using standard audiological procedures (AzBio Quiet, AzBio +5/+10dB; CNC 50-item list)

- Obtain patient reported outcome questionnaires (SSQ-12 and CIQOL)
- Conduct integrity evaluation of device using telemetry
- Review of adverse events since the last visit

Schedule of Events Table							
	Baseline	Week 2 (televisit)	Week 3 (televisit)	Week 4 (televisit)	Week 5 (televisit)	1 month post- assessment (in-office visit)	6 month post - assessment (in-office visit)
	Visit 1	Visit 2	Visit 3	Visit 4	Visit 5	Visit 6	Visit 7
Consent	X						
Hearing and Speech Reception Thresholds	X					X	X
Patient Reported Outcome Measures (SSQ12 and CIQOL)	X					X	X
Auditory Training in office – establish therapy plan	X	X					
In-office tDCS – establish protocol, patient training	X						
Home Auditory training and tDCS (daily)					→		
Weekly video visit to review use & compliance of training		X	X	X	X		
Review of symptoms and adverse events		X	X	X	X	X	X
Subject Compensation	X					X	X

6) **Selection of Subjects:**

Inclusion Criteria

1. Age \geq 18 years of age
2. Patients with a unilateral Cochlear Implant device in use for a minimum of 1 year

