It's possible that tDCS pads may cause damage to hearing aid microphones if they get wet. Therefore, participants who wear a contralateral hearing aid will be instructed to remove it prior to and during the use of tDCS.

Participants will record daily symptoms via a link to a REDCap survey. REDCap will be programmed to alert the PI and/or SC of symptoms with an intensity level reported at 8 or above on the AE/symptom survey, regardless of the duration indicated (refer to table below). The PI, SC, or delegate will contact the patient to obtain additional information and determine if tDCS should be discontinued, and if a referral for medical evaluation is needed.

In conclusion, given the low risk of tDCS and its combination with CI, the risk/benefit is favorable since improvement in the patients’ speech perception due to the administration of tDCS could improve their quality of life.

12) Costs to the Subject:

The study does not involve any costs to subjects. Costs for the audiological assessments will be covered by the study. tDCS devices for in-home use will be provided to study participants at no charge and returned at the end of the 1-month follow-up visit.

13) Data Analysis & Statistical Considerations:

The primary outcome measures of feasibility are: 1) proportion of eligible CI patients who expressed interest in the study; 2) proportion of selected participants who completed tDCS training and demonstrated competence in the office and subsequently at home during remote visits; 3) proportion of participants who completed most or all of the proposed intervention protocol; 4) proportion who completed relevant appointments, and reasons for any missing data; 5) acceptability of patient incentive; 6) patient report of ease/difficulty carrying out the protocol via a patient survey at Visit 2; 7) proportion of people with any adverse events, and 8) other feasibility and acceptability metrics consistent with the latest guidelines on pilot studies (Eldridge et al. 2016). After each in-office tDCS application and at the immediate one month post-intervention Visit 6, the site of tDCS stimulation and the CI site will be visually examined for any skin irritation or tenderness and the internal and external CI devices will be examined for signs of abnormal function. Adverse effects of tDCS will be measured by the intensity and duration of symptoms recorded on the daily diary.

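### Patient-rated ease of carrying out the protocol (feasibility item 6) is surveyed only at Visit 2, so it supports a statement about early use, not about the four-week home course

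*Combined protocol and SAP*

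**What the plan says.** Purpose (a) in section 2 opens: "To evaluate the safety and feasibility of reliable Transcranial Direct Current Stimulation (tDCS) administration at home", combined with training at home. Section 13 then lists eight primary feasibility outcomes. The sixth is "patient report of ease/difficulty carrying out the protocol via a patient survey at Visit 2".

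The Schedule of Events in section 5 labels Visit 2 as the week-2 televisit, the first of four weekly televisits. During weeks 2 to 5 participants are to "Complete daily web-based auditory training with tDCS stimulation for 30-minute sessions, at least five times per week for 4 weeks". Section 14 dates the start of this training to week 2.

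Other information is gathered throughout the home phase:

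- Section 5 asks for "Completion of a daily diary to record compliance of auditory training with tDCS, as well as to document adverse events".
- Section 5 also requires video visits at least weekly "to provide technical assistance as needed, review reported adverse events, and give reminders regarding completion of the daily diary".
- Section 4 says of the tDCS unit: "The device also allows the clinical team to control and monitor the home use by the patient".
- Section 13 includes competence at remote visits (item 2), completion (item 3), attendance (item 4), adverse events (item 7) and an open-ended category of other metrics (item 8).
- Section 15 records the reason for and date of any withdrawal.

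The questionnaires named for Visits 6 and 7 are SSQ-12 and CIQOL.

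**The concern.** The course under study lasts four weeks, yet the one outcome described as asking participants how easy or hard it was is taken near its beginning. Completion and competence show that participants did the sessions and were able to do them. They do not show how hard the sessions were to fit in and keep up, and a participant can finish every session and still find the regimen difficult.

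The plan itself gives reasons why an early rating may not represent the course. Video visits are more frequent in the first week, so support may be densest when the survey is taken. The schedule also marks Visit 2 for establishing the therapy plan, so set-up may still be under way. The training programs adjust their difficulty to performance, so the task changes over time. Ease could improve with practice or worsen with fatigue, and one early rating cannot show which.

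At stake is what the team can report under item 6 and carry into a later trial. A rating not taken near the end of the course cannot be recovered reliably afterwards.

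**Working it through.** The plan gives no figure to reproduce here, so the check is one of timing.

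**Inputs**
- Minimum intensity: 5 sessions a week for 4 weeks (section 5).
- Visit 2 in week 2 and Visit 5 in week 5 (Schedule of Events, section 5).
- Start of training with tDCS at week 2 (section 14).
- Up to 14 enrolled, allowing for 4 drop-outs (section 7).

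**Minimum course:** 5 × 4 = 20 sessions.

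**Sessions done by Visit 2, week-2 start.** Visit 2 falls somewhere in the first training week, so zero to one full week is done:
- Visit at the start of the week: 5 × 0 = 0 of 20 (0%).
- Visit at the end of the week: 5 × 1 = 5 of 20 (25%).
- Still to come: 15 to 20 of 20 (75% to 100%).

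**Sensitivity to more frequent use.** Five a week is a minimum. Assume at most one session a day. The most front-loaded pattern is seven in the first week and five in each of the others: 7/(7 + 5 + 5 + 5) = 7/22 = 32%. That leaves 15/22 = 68%.

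**Sensitivity to the start date.** Section 5 says "Enrolled participants will be given a tDCS device to take home to complete study procedures", so a reader might suppose that home use begins straight after baseline. This is an assumption against section 14. One to two full weeks would then be done by Visit 2: 5/20 to 10/20, or 25% to 50%. The most front-loaded pattern gives 14/(7 + 7 + 5 + 5) = 14/24 = 58%, leaving 10/24 = 42%. The home-training row of the schedule survives in the extracted text only as an arrow, so it cannot settle the start.

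**Is a later rating named anywhere?**

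| Source | Described content | Asks about ease? |
|---|---|---|
| Daily diary | Compliance, adverse events | Not described |
| Weekly video visits | Technical help, use and compliance, adverse events, diary reminders | Not described |
| Visits 6 and 7 questionnaires | SSQ-12, CIQOL | Not described |
| Items 2, 3, 4, 7 | Competence, completion, attendance, adverse events | No |
| Item 8 | Unspecified other metrics | Possible, but no instrument or visit named |

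Section 13 also compares survey results at 1 and 6 months with baseline. That sentence concerns efficacy, so it reads as SSQ-12 and CIQOL.

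**Where a second rating could go.** With a week-2 start, Visit 5 falls in the fourth training week. Between 5 × 3 = 15 and 5 × 4 = 20 of 20 sessions (75% to 100%) are then done. Visit 6 is described in two ways. The text of section 5 says "Participants will be asked to return at the end of the 30-day treatment period for an in-person visit", but the heading above it places the visit one month after treatment, and the baseline text also calls it a post-treatment visit at one month. Section 13 calls the visit immediate and one month post-intervention in the same phrase.

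**Effect of drop-out on a later rating.** With 4 losses from 14 (4/14 = 29%), at most 10 of 14 (71%) give an end-of-course rating. As an illustration, suppose all 10 completers find the protocol easy and all 4 who left found it hard. Completers alone give 10/10 = 100%, and all enrolled give 10/14 = 71%.

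**The case against.** The strongest reply is that feasibility over the whole course is already well covered. Completion, competence, attendance, adverse events, the diary, the weekly contacts, device monitoring and withdrawal reasons all extend beyond Visit 2, and item 8 leaves room for more. Section 13 attaches no threshold to item 6 and reports plain proportions. It never says that item 6 will carry a claim about ease over four weeks. An early survey is also useful in itself for set-up and learning problems.

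Most of this stands, and it limits the point to a minor one. A reader might infer that the plan does not assess feasibility beyond the first week. The documents do not support that, because only the patient's own rating of ease lacks later coverage. A reader might also infer that a later rating is ruled out. It is not, since item 8 is open-ended. The survey instrument and the symptom table mentioned in section 11 are not in the extracted text, so the absence of a later rating is read from the prose alone. What remains is that the plan names one time for this outcome, that time is early, and nothing comparable is named at the end.

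**Conclusion.** The point holds as a minor one. On the section 14 start date, item 6 is rated after about 0 to 5 of the 20 minimum sessions, so on its own it supports a statement about early use. Under the least favourable assumptions on start date and frequency, 42% of sessions would still follow the survey, so the rating would not cover the full course in that case either.

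The size rests on a steady minimum rate and on Visit 2 falling within week 2. No sample size, safety result or efficacy result depends on it. The documents do not show that ease changes over the course or in which direction, so it would go too far to say that the Visit 2 rating is biased. Nor is the early survey a mistake: it is insufficient by itself for a four-week statement.

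**What to change.** 1. Reconcile the descriptions of Visit 6 in sections 5 and 13. If it falls a month after the last session, a rating taken there would rest on recall.
2. Keep the Visit 2 survey, labelled as an early-use measure.
3. Repeat the same survey once at the end of the four-week course, at a contact already scheduled: the Visit 5 televisit if the course is then complete or nearly so, or Visit 6 if it is confirmed to fall at the end of treatment.
4. Seek the same rating from participants who stop early. Report end-of-course and early-stop ratings side by side, each with the number rated out of the number enrolled, and state that ratings from completers alone may look favourable.
5. Add the survey to the Schedule of Events, which has no row for it even at Visit 2.

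Possible wording for item 6: *patient-rated ease or difficulty, by the same survey at Visit 2 (early use) and once at the end of the home course, with early-stop ratings reported alongside.*

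The cost is one more short questionnaire for each of up to 14 participants, a line of text and a table row. Some ratings from drop-outs will still be missing. If the team prefers not to add a survey, describing item 6 as early-use ease would at least match the claim to the data.

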tDCS uses low voltage (typically < 20 V) and direct currents (typically < 2 mA) applied through scalp surface electrodes. Thus, it is comparable to connecting a conventional 9 V battery to the electrodes. The low voltages and currents contribute to an excellent safety profile of tDCS. According to a recent review paper (Bikson et al 2016) there are no known long-term health risks from the use of tDCS, *per se*, when operated within consensus safety guidelines. However, minimal, acute side effects of tDCS may include discomfort, skin irritation, lightheadedness, and headache.

- *Potential risk of skin irritation.* The most commonly reported side effect is skin irritation at the sites of the tDCS electrodes. This may include reddening of the skin underneath the electrodes or itching at the site of stimulation. Skin lesions, such as burn-like lesions or contact dermatitis, have also been observed.
- *Potential risk of lightheadedness.* While rare, feelings of pre-syncope, or lightheadedness, with stimulation can occur. This condition can sometimes occur during the “ramp-up” or “ramp-down” phase at the beginning and end of the protocol as the current is changing.
- *Potential risk of headache.* A potential side effect of tDCS is a headache that could develop during or immediately after the stimulation and may last for minutes to hours following the end of the stimulation. It is typically limited to the day of stimulation, and usually responds promptly to single doses of over-the-counter analgesics.
- *Potential risk of impairments in cognitive function.* There has been no evidence of neuronal damage or cognitive impairment induced by tDCS as demonstrated in Nitsche and Paulus (2001) and Nitsche et al. (2003).

As noted above, the primary side effects of tDCS are mostly related to interactions between the electrodes and the scalp skin. These side effects however are mitigated by the proper selection and application of the electrodes. To minimize chemical reactions at the electrode–skin interface, non-metallic, conductive rubber electrodes, covered completely with saline-saturated sponges will be used in this study, as recommended by Nitsche and Paulus, 2000. The electrodes will be single-use and packaged for convenient and safe use at home by the patients.

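### No skin inspection is scheduled during the home tDCS course, so skin reactions that clear before Visit 6 reach the results by self-report only

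*Combined protocol and SAP*

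**What the plan says.** Section 2 makes the safety and feasibility of tDCS given at home the first purpose of the study. Section 11 states: "The most commonly reported side effect is skin irritation at the sites of the tDCS electrodes". It adds: "Skin lesions, such as burn-like lesions or contact dermatitis, have also been observed".

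Section 13 gives the timing and the sites of the inspection: "After each in-office tDCS application and at the immediate one month post-intervention Visit 6, the site of tDCS stimulation and the CI site". What is done there is a look by an observer; both places "will be visually examined for any skin irritation or tenderness". The examiner is not named. In the Section 5 schedule table, the row "In-office tDCS – establish protocol, patient training" is marked at Visit 1 only.

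For the home period, Section 5 asks participants to "Complete daily web-based auditory training with tDCS stimulation for 30-minute sessions, at least five times per week for 4 weeks". During those weeks, "Video visits will be conducted at least weekly by a member of the research team, starting more frequently in the first week"; their listed content is technical help, review of reported adverse events and diary reminders. Section 11 adds a daily symptom survey, with an alert to the study team at intensity 8 or above and possible referral for medical evaluation.

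Section 13 measures adverse effects of tDCS by the intensity and duration entered in the diary. It lists the proportion of people with any adverse event as feasibility outcome 7, and plans the prevalence of reported effects overall and by time window.

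**The concern.** The inspection and the exposure fall at different times. The harm named as commonest is local to the skin and tied to sessions, and nearly all sessions take place at home. An observer is required to look at the sites only before the home course begins and after it has ended.

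In between, a reaction is counted only if the participant notices it and records or mentions it. The target is the auditory cortex on the side opposite the implant (Section 4). That puts an electrode on the side of the head, where the wearer cannot look directly. Painless redness or a small lesion there may go unrecorded, and need not reach intensity 8.

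What is at stake is the completeness of outcome 7 and of the time-window prevalence for the home weeks, the period that the study's safety statement is about.

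**Working it through.** **Planned inspections per participant**
- In-office tDCS, from the schedule table: Visit 1 only. Visit 2 is also ticked for in-office auditory training, but that row is not tDCS and the column is a televisit.
- Visit 6: one inspection, from Section 13.
- Total: 1 + 1 = 2. Between the first home session and Visit 6: 0. After the whole home course: 1.

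Section 14 starts adverse-event monitoring with the training at week 2, so of these two inspections only the one at Visit 6 lies inside the stated monitoring window.

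**Home exposure**
- Per participant: 5 sessions per week × 4 weeks = at least 20.
- Ten completers: 10 × 20 = at least 200. Fourteen enrolled (the Section 7 maximum): 14 × 20 = 280.

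**What Visit 6 can see**
The Visit 6 text in Section 5 reads "Participants will be asked to return at the end of the 30-day treatment period for an in-person visit", and Section 13 calls the visit immediate. Its heading in Section 5 places it one month post-treatment. On either reading it follows the home sessions. On the first it can show reactions from the last sessions and anything persistent; on the second, short-lived reactions would have gone. The Section 5 list for Visit 6 has telemetry and adverse-event review but not the skin examination that Section 13 assigns to it.

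**How many participants could have a reaction at home**
The documents give no per-session rate *p*, so this is an assumption shown as a range. With independent sessions, P(at least one in 20) = 1 − (1 − *p*)^20.
- *p* = 1%: 1 − 0.99^20 = 0.18
- *p* = 5%: 1 − 0.95^20 = 0.64
- *p* = 10%: 1 − 0.90^20 = 0.88

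If reactions cluster in some participants, these proportions are lower for the same average rate. They count participants with a reaction, not participants whose reaction is missed. The latter also depends on the share that goes unreported and clears before Visit 6, for which there is no figure.

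**Effect on outcome 7**
With 10 participants, each one wrongly counted as free of adverse events moves the proportion by 1/10 = 10 points; with 14, by 1/14 = 7 points. This applies only to a participant with no other recorded adverse event, since outcome 7 counts any event.

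**The case against.** The strongest reply is that the plan does not rely on inspection. Tolerability is measured from the diary. A home reaction that has cleared by Visit 6 still counts if it was entered, and a clean inspection cannot cancel a diary entry. The home weeks also have the continuous questionnaire reviewed at each televisit, the intensity-8 alert, a device that lets the team monitor use, competence to be shown at remote visits (outcome 2) and frequent team review of reported events. The symptom table that Section 11 refers to is not in the text available, so the survey may prompt specifically for skin changes. All of this stands, and it confines the point to reactions that are not noticed or not reported.

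The assumed rates can also be challenged. Section 11 cites 191 sessions in healthy volunteers with no adverse events; at 5% per session the chance of none would be 0.95^191, about 0.00006. But that was another population with about 191/69 = 2.8 sessions each, and the same section lists redness among the commonest effects in a depression trial. The rate is unknown, and the gap does not depend on which value holds.

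The proposed remedy is partial. Four weekly looks cover about 4/20 = 20% of the minimum number of sessions. At 5% per session, if each look follows a session and reactions are gone before the next look, 1 − 0.95^4 = 19% of participants would be seen with a reaction, against 64% affected. This stands too: the look adds to self-report and does not replace it.

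Two stronger readings are tempting. A reader might infer that no home session is ever followed by an examination; that is wrong, because Visit 6 follows the whole course. A reader might also infer that a near-zero inspection result could carry a false safety conclusion; the documents plan no separate inspected-reaction proportion, so this is not supported.

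**Conclusion.** The point holds in a limited form. No inspection of the stimulation or CI site is scheduled between Visit 1 and Visit 6, across at least 20 home sessions per participant. Skin reactions that begin at home and clear before Visit 6 enter outcome 7 and the time-window prevalence through self-report alone. The likely error is under-counting of reactions the wearer does not notice or does not report. Its size cannot be computed from the documents: the 18% to 88% range rests on assumed rates of 1% to 10% and on independent sessions, and it describes occurrence, not omission.

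This is a cheap improvement to what is measured in a small single-arm feasibility study, not a fault that invalidates the plan. The two statements about the timing of Visit 6, and the two about its content, do not agree and need to be reconciled whether or not the improvement is adopted.

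**What to change.** - In Section 5 (Visits 2–5) and Section 13, add a brief on-camera look at the electrode sites and the CI site at each existing weekly video visit, timed after a session where possible. Record each site as reaction present or absent, with a simple grade.
- In Section 13, report observer-seen reactions for the home period alongside the diary-reported ones, not instead of them.
- Reconcile the Section 5 list for Visit 6 with the skin examination that Section 13 assigns to that visit.
- Reconcile the one-month post-treatment heading of Visit 6 with the text that sets it at the end of treatment, so that the interval from last session to inspection is known.

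Cost: a minute or two per existing video visit and one form field, with no new visit or staff. Downsides: a camera view through hair is less sensitive than an in-person look, it cannot assess tenderness, and it samples only about 4 of the 20 or more sessions.
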